## Implementation and process evaluation

### Research objectives

A synthesis of quantitative and qualitative analysis will be used to address key objectives addressing the implementation, process and equity associated with the intervention. The focus of this is to assess: the extent to which the intervention has been implemented as intended including factors that facilitate or hinder implementation; the acceptability of the intervention from the perspectives of participants, staff and key stakeholders; the impact of dosage, adherence and staff turnover on outcomes observed; the extent to which the findings are generalisable to the wider population, particularly in terms of ethnicity and equity; and to identify positive and negative experiences associated with the intervention and when they occur.

### Research Questions

The IPE is framed in 7 research questions:

1. To what extent do staff within services adhere to the intended delivery model?
2. What factors facilitate or hinder intervention delivery?
3. How acceptable is the intervention from the perspective of participants, staff and key stakeholders?
4. How is the 'dose' of, and adherence to, the intervention associated to outcomes observed?
5. How generalisable are the findings to the wider population accessing the services?
6. What positive or negative experiences do participants and staff highlight and when do these occur?
7. Do changes in the behaviour change model occur as hypothesised?

**Table 4: IPE methods overview**

IPE Question	Data collection methods	Participants/ data sources (type, number)	Data analysis methods	Research questions addressed	Implementation/ logic model relevance
--------------	-------------------------	---	-----------------------	------------------------------	---------------------------------------

IPE.Q1	Process data regarding interventions planned and delivered.	Receipt of initial case formulation in accordance with identified tier of need. Session data highlighting components of intervention planned versus components delivered.	Descriptive statistics.	To what extent do staff within services adhere to the intended delivery model?	Adherence to the delivery model leads to better outcomes.
IPE.Q2	Semi-structured interviews addressing facilitators and hindrances associated with intervention delivery, and factors associated with non-compliance.	20 staff members, 10 participants and 10 parent/carers purposively sampled by service, age and ethnicity.	Inductive thematic analysis. Findings will be mapped onto NPT.	What factors facilitate or hinder intervention delivery?	Understanding what factors facilitate or hinder engagement with the intervention can identify modifications that can be made.
IPE.Q3	Semi-structured interviews addressing acceptability.	20 staff members, 20 participants and 10 parent/carers and 10 key stakeholders (clinical psychologists, inter-agency workers) purposively sampled by service, age and ethnicity.	Inductive thematic analysis. Findings will be mapped onto NPT.	How acceptable is the intervention from the perspective of participants, staff and key stakeholders?	Understanding acceptability can lead to modifications that increase engagement and have better outcomes.
IPE.Q4	Quantitative analytical model exploring the role of 'dose' on outcome observed,	Session data, intervention participants survey data,	Stratified regression analysis to explore the relationship of 'dose' on	How is the 'dose' of, and adherence to, the intervention associated to	Does the 'dose' of intervention stratified by tier have an impact on

	service staff turnover and staff wellbeing.	staff turnover and wellbeing.	outcomes controlling for potentially confounding factors, including allocated tier.	outcomes observed?	outcomes observed.
IPE.Q5	Semi-structured interviews focussing on the appropriateness of referral process and explore whether some groups are unable to access the service.	20 semi-structured interviews with participants, 20 interviews with practitioners and 20 semi-structured interviews with key stakeholders, 10 of which will be parents/ carers. Purposively sampled to get variety by service, age, and ethnicity	Inductive thematic analysis Findings will be mapped onto NPT.	How generalisable are the findings to the wider population accessing the services?	The intervention has to be accessible by all potential participants.
IPE.Q6	Semi-structured interviews focussing on the positive and negative experiences of the intervention and when these occur.	20 semi-structured interviews with participants, 20 interviews with practitioners and 20 semi-structured interviews with key stakeholders, 10 of which will be parents/ carers. Purposively sampled to get variety by	Inductive thematic analysis. Findings will be mapped onto NPT.	What positive or negative experiences do participants and staff highlight and when do these occur?	Identify potential modifications that can be made to maximise the impact of the intervention.

		service, age, and ethnicity.			
IPE Q7	Semi-structured interviews focussing on perceptions of what change has occurred.	20 semi-structured interviews with participants, 20 interviews with practitioners and 10 semi-structured interviews with parents/ carers. Purposively sampled to get variety by service, age, and ethnicity.	Inductive thematic analysis. Findings will be mapped onto NPT.	Do changes in the behaviour change model occur as hypothesised?	Is the ToC a valid representation of what changes actually occur.

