Practitioners engage in trauma screening for any young person allocated to the intervention arm, and dependent on the young person's need the intensity of intervention is agreed. Tier 1, the lowest tier of need, includes young people who have evidence of past trauma, but it is not complex (it may be due to temporary family or financial difficulties for example), and they have experienced periods of recovery. Tier 2 involves young people who have more complex trauma with little evidence of periods of recovery, often a result of family breakdown or significant traumatic events; these young people require more intensive intervention involving an in-house multi-disciplinary team. Young people in tier 3 are the most complex, they will have a significant history of trauma, often as a result of neglect, breakdown, or involvement in criminal activity, with no evidence of any periods of recovery, and intervention needs to be both multi-disciplinary and led by a clinical psychologist. A brief comparison of BAU and different tiers of intervention is provided in table 2 and more detail provided below.

Tier 1 involves guidance and support from the trauma leads to the case manager and other relevant professionals involved in the case, on engaging with and supporting the young person in a trauma-informed manner. The trauma leads assist to ensure that assessments and reports are conducted with a trauma-informed perspective. This involves considering the young person's trauma history, understanding the potential triggers, and incorporating trauma-related information into the assessment process. This approach helps to gain a comprehensive understanding of the young person's needs and informs the development of an effective intervention plan. Trauma leads will review the progress of interventions mid-intervention against the Trauma Recovery Model (TRM) framework. This assessment helps identify any necessary adjustments or modifications in the intervention plan, ensuring that it remains responsive to the young person's evolving needs and progress.

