The interviews aim to capture diverse perceptions of the intervention, utilising Normalisation Process Theory (NPT). This approach will facilitate mapping findings onto NPT's constructs: coherence (how the intervention is perceived and understood), cognitive participation (engagement and commitment of stakeholders), collective action (integration of the intervention into practice), and reflexive monitoring (ongoing assessment and adaptation of the intervention). Bracketing, reflexivity, and member checking will be integral to ensuring research trustworthiness and rigour.

Data will be analysed using NVivo software, employing an inductive approach without the constraint of existing theories, to allow for the natural emergence of findings. This analysis aims to identify critical elements of the intervention, explore implementation issues, and understand ethnicity and equity concerns. It will also focus on identifying perceived barriers or facilitators to implementation in usual practice. This inductive analysis, grounded in the data, will contribute valuable insights into the practicalities of the implementation process.

We propose to augment the qualitative analysis with the secondary quantitative analysis, detailed in the analysis section on page 19, to explore how content, compliance, and therapeutic alliance impact on the outcomes observed. A regression model will be conducted, with the primary outcome, number of offences in the previous 6-months, as dependent variable and adjusting for key covariates identified. This will allow for a quantification of what dimensions of the intervention are associated with outcomes and will enable an exploration of whether certain domains are more important than others and should be emphasised in the intervention delivery and, by extension, the training. Allied to this, we will assess the impact of staff turnover across the services, wellbeing of practitioners and the extent to which staff perceptions of working in a trauma informed manner, assessed using ARTIC 35, influences outcomes. In addition, the perception of therapeutic alliance will provide an insight into whether therapist communication style influences outcomes.

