Practitioners engage in trauma screening for any young person allocated to the intervention arm, and dependent on the young person's need the intensity of intervention is agreed. Tier 1, the lowest tier of need, includes young people who have evidence of past trauma, but it is not complex (it may be due to temporary family or financial difficulties for example), and they have experienced periods of recovery. Tier 2 involves young people who have more complex trauma with little evidence of periods of recovery, often a result of family breakdown or significant traumatic events; these young people require more intensive intervention involving an in-house multi-disciplinary team. Young people in tier 3 are the most complex; they will have a significant history of trauma, often as a result of neglect, breakdown, or involvement in criminal activity, with no evidence of any periods of recovery, and intervention needs to be both multi-disciplinary and led by a clinical psychologist.

Tier 1 involves guidance and support from the trauma leads to the case manager and other relevant professionals involved in the case, on engaging with and supporting the young person in a trauma-informed manner. The trauma leads assist to ensure that assessments and reports are conducted with a trauma-informed perspective. This involves considering the young person's trauma history, understanding the potential triggers, and incorporating trauma-related information into the assessment process. This approach helps to gain a comprehensive understanding of the young person's needs and informs the development of an effective intervention plan. Trauma leads will review the progress of interventions mid-intervention against the Trauma Recovery Model (TRM) framework. This assessment helps identify any necessary adjustments or modifications in the intervention plan, ensuring that it remains responsive to the young person's evolving needs and progress.

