To explore the proposed mechanism of change we will conduct a prognostic linear regression analysis to model the relationship between pre-randomisation factors; age, gender, ethnicity, IMD, SRDS, SDQ, BFRS, GHQ and observed outcomes at 6- and 12- months respectively on the primary outcome at either 6- or 12-months. Interaction terms with allocation arm will be included in the analysis, and a significance level of 0.1 will be used to determine which factors are to be included in the regression model. This analysis will be augmented by an additional

analysis including participants in the RBT arm only using the same pre-randomisation factors but also including process measures of compliance, therapeutic alliance, and interventionist attitude to trauma informed practice.

Interim analyses and stopping rules

No interim analyses are planned. The trial will only be stopped if evidence emerges of a serious adverse event associated with participation in the trial. As the intervention has already been implemented in practice with youth offending populations there is no evidence at the outset that a serious adverse event is likely to occur.

Longitudinal follow-up analyses

Assessments are conducted at baseline, prior to randomisation and then again at months 6 and 12, with 6-months being considered the primary endpoint. Table 2 provides an overview of what measures are being conducted at each time-point.

Outcome	No of items	Baseline	Six months	Twelve months
Primary				
Self-reported delinquency (SRDS) ¹	36	✓	✓	✓
Secondary				
Strength and Difficulties (SDQ) ¹	25	✓	✓	✓
Wellbeing (SWEBWMS)	7	✓	✓	✓
Psychological Distress (GHQ12)	12	✓	✓	✓
Family environment (BFRQ)	16	✓	✓	✓
Receipt Inventory (CSRI)	8	✓	✓	✓
Staff attitudes to trauma informed care (ARTIC)	35	✓	✓	✓
Staff wellbeing (SWEBWMS)	7	✓	✓	✓
Staff turnover & absence	2	✓	✓	✓
Exploratory				
Adverse childhood experiences (ACE-Q)	10	✓		
Process				
Therapeutic relationship	12		✓	
Proportion of sessions planned & delivered	1		✓	✓

Imbalance at baseline

Rather than just assume the randomisation has worked, we will assess observed balance by comparing the means and distributions of the groups created by randomisation for both participants and staff. If they are systematically different across those variables we observe – e.g. always larger / smaller in one group - then that would suggest the randomisation has not been successfully implemented. Baseline equivalence following randomisation will be

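### The protocol's dose regression is to control for allocated tier, but the SAP's RBT-arm regression on compliance leaves tier out, so its associations may partly reflect need

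*Protocol*

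**What the plan says.** **Protocol, Table 4, IPE.Q4.** The planned method is a stratified regression of dose on "outcomes controlling for potentially confounding factors, including allocated tier". The matching logic-model entry asks: "Does the 'dose' of intervention stratified by tier have an impact on" the outcomes.

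**Protocol, Research Methods.** A regression with offences in the previous six months as dependent variable covers content, compliance and alliance. It adjusts for key covariates that this section does not list. The protocol says that it "will enable an exploration of whether certain domains are more important than others and should be emphasised in the intervention delivery" and in the training.

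**SAP, Further analyses.** The prognostic model uses "pre-randomisation factors; age, gender, ethnicity, IMD, SRDS, SDQ, BFRS, GHQ", and "a significance level of 0.1 will be used to determine which factors are to be included in the regression model". A further analysis in the RBT arm alone takes the same baseline factors "but also including process measures of compliance, therapeutic alliance, and interventionist attitude to trauma informed practice". Tier is not in either list. The SAP mentions tier only when it describes the intervention.

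**How tier arises.** In the RBT arm, young people are screened after randomisation and, "dependent on the young person's need the intensity of intervention is agreed" (SAP, Intervention). The trauma history in tier 3 is described as "often as a result of neglect, breakdown, or involvement in criminal activity" (Protocol, Intervention). In the protocol's table comparing the tiers with BAU, the multi-agency case formulation meeting appears only in tiers 2 and 3, and psychologist leadership only in tier 3.

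**The concern.** Within the RBT arm, compliance and components are not randomised. Tier is a summary of need made before the sessions begin, it is plausibly related to later offending, and it determines what a young person is offered. The protocol treats it as a confounder by name. The SAP model that carries compliance, alliance and staff attitude drops it.

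The listed baseline scores are a partial substitute. Tiers are described by complexity of trauma and by periods of recovery, which SRDS, SDQ, BFRS and GHQ do not measure directly. The nearest baseline measure, adverse childhood experiences, is in the protocol's list for Objective 5 but not in the SAP's list. Service, which the protocol's Analysis section treats as an ordering of complexity, is missing from that list too.

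At stake is the reading of a process analysis that is meant to guide delivery and training. A component offered only to the most complex cases could look unhelpful because of who receives it, and a dose association could appear where there is none.

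**Working it through.** **1. Covariates side by side**

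| | Protocol Table 4, IPE.Q4 | Protocol, Research Methods | SAP, RBT-arm model |
|---|---|---|---|
| Dose or compliance | yes | yes | yes |
| Therapeutic alliance | not named | yes | yes |
| Staff attitude | not named | yes (ARTIC) | yes |
| Staff turnover and wellbeing | yes | yes | no |
| Allocated tier | yes | covariates not listed | no |
| ACE, service | not named | covariates not listed | no |

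**2. Size of the RBT-arm model.** The plan's figure reproduces. For d = 0.25, two-sided alpha 0.05 and 80% power, the noncentral t calculation gives 253 per arm (power 0.801), so 506 in total, and 506/0.9 = 562.2 against the stated 562. The model would therefore have about 253 people at month 6.

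**3. Bias from leaving tier out.** Let r be the correlation of tier with the outcome that remains after the other covariates, and ρ the correlation of tier with dose. With no true dose effect, the expected standardised dose slope without tier is r × ρ. The test statistic is centred at about √253 × rρ / √(1 − (rρ)²). For r = 0.3 and ρ = −0.4, rρ = −0.12 and 15.9 × 0.12 / √(1 − 0.0144) = 1.92 in absolute value. The chance of passing 1.645 is then about 61%. Simulation (3,000 runs per row, assumed tier shares 50/30/20%) agrees:

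| r | ρ | slope without tier | false positives at 0.10 without tier | with tier |
|---|---|---|---|---|
| 0.1 | −0.2 | −0.02 | 11% | 9% |
| 0.2 | −0.2 | −0.04 | 18% | 11% |
| 0.2 | −0.4 | −0.08 | 35% | 10% |
| 0.3 | −0.4 | −0.12 | 61% | 10% |

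With tier in the model the slope is 0.00 in every row. If r or ρ is zero there is no bias either way. The 0.10 level is the SAP's selection level. The SAP does not say outright that it carries over to the RBT-arm model.

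**4. How far the baseline scores help.** A second simulation used counts: 253 people, assumed tier shares 50/35/15%, attendance SD 20 points, negative binomial counts with dispersion 1, adjustment for baseline count, and a test at 0.05. Neither document gives a pre/post correlation for SRDS, so individual persistence in offending is varied.

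| Mean offences; attendance by tier | no persistence | frailty correlation 0.5 | same, plus three need proxies | full persistence |
|---|---|---|---|---|
| 2/4/7; 75/65/50% | 54% | 28% | 17% | 10% |
| 2/3/4.5; 75/65/50% | 30% | 18% | 11% | 8% |
| 2/3/4.5; 70/65/60% | 10% | 8% | 5% | 7% |

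The proxies stand in for SDQ, BFRS and GHQ and are assumed to shift by 0.5 SD per tier. With tier in the model the rate is 5–6%. In the worst cell the false slope is −0.60 offences per 20 points of attendance. The overall mean there is 0.50×2 + 0.35×4 + 0.15×7 = 3.45, so the slope is 17% of the mean. With full persistence it falls to −0.10.

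**The case against.** Several objections stand, and they set the limits of the point.

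- **The SAP has other dose analyses.** Its Compliance section plans CACE at five thresholds with allocation as the instrument, and the protocol names CACE as its unbiased route to the role of dosage. These compare randomised groups, so tier does not confound them.
- **The match is inferred.** The SAP does not label its RBT-arm model as IPE.Q4, and that model lacks the staff turnover and wellbeing terms of IPE.Q4. The link rests on the shared process terms and on the protocol's deferral of analysis detail to the SAP.
- **The Research Methods regression is not clearly deficient.** It leaves its covariates open, and Table 4 in the same part of the protocol names tier.
- **Tier does not raise dose mechanically.** Participant dose is the share of planned meetings attended, scaled to each plan. A link between tier and attendance is an assumption. The confounding is most direct for components and fidelity.
- **Criminal involvement is not a tier criterion.** The text gives it as one frequent source of the trauma seen in tier 3.

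A reader might also take Table 4's stratified regression to mean separate fits by tier, with too few people in tier 3. The same cell speaks of controlling for tier, which a single model can do, and the documents give no tier shares. That reading is not supported.

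None of this puts tier into the SAP's list.

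**Conclusion.** The omission is real and confined to a secondary process analysis. The protocol names tier as a confounder of the dose–outcome relation, and the SAP's explicit list for the RBT-arm model leaves it out. As written, associations of compliance or components with offending in that model may partly reflect need.

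The size is not known. Under the assumptions shown, the false-positive rate without tier runs from near nominal to above 50%. The upper figures need a strong link of tier to both outcome and dose, and baseline scores that capture little of the need. Adding tier brings the rate back to about nominal.

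A reader might infer that need will be mistaken for a dose effect, or that 54% or 61% is the expected error rate. The documents support neither: they give no tier–outcome or tier–dose correlation, and the protocol itself speaks of association. The primary ITT analysis and the CACE analyses do not depend on this point.

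**What to change.** 1. **SAP, Further analyses.** Force allocated tier into the RBT-arm model as a factor, exempt from the 0.1 selection rule. Add a separate level for participants not screened and so without a tier. The SAP's Compliance section expects such participants, and a three-level factor would drop them, which selects on the exposure being studied. Report how many fall in this level.
2. **Protocol, Research Methods.** State that tier is among the key covariates. State that components belonging only to certain tiers are compared within tier, as delivered versus planned.
3. **Both documents.** Report these results as associations.

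Conditioning on tier is acceptable here: the model lies within one arm, so no randomised comparison is broken, and tier is set before the sessions start. The cost is wording and three degrees of freedom (two if everyone is screened). Tier is already assigned for every screened participant and is needed for IPE.Q1, so no new data are required.

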## Research Methods

The qualitative component of the study will be purposive and include semi-structured interviews with at least 20 young people, 20 intervention delivery staff and 20 key stakeholders to answer IPE Q2, Q3, Q5, Q6 and Q7. The key stakeholders would include 10 parents/carers, and 10 staff from key services involved, such as the psychology team linked to the All-Wales Forensic Adolescent Consultation and Treatment Service (FACTS) and staff from other services who become involved in formulation and trauma planning and who are invited to create the trauma intervention (e.g., relevant multi-agency partners such as education, children social care, and police). Participants will be chosen purposively to provide diversity in terms of service and age, and ensure appropriate participation by sex and ethnicity to explore issues of equity and inclusion. Although a total sample of 60 interviews will be the aim, the sample size considerations of the qualitative component are driven by the need to achieve data saturation, and this needs to be judged in practice rather than stated in advance.

Semi-structured interviews will be conducted between month 7 and month 28, either online or face-to-face, as appropriate. A research associate will interview each participant once, and within that interview we will explore each of the relevant IPE research questions.

All interviews will be recorded, with consent, and transcribed verbatim. Inductive thematic analysis (Braun & Clarke, 2006) will be used to analyse the narrative accounts, with the understanding that saturation will guide the requisite sample size, which cannot be predetermined. If saturation is not achieved, an additional 5-10 stakeholders may be

recruited. Efforts will be made to incorporate views from those who dropped out or were non-compliant with the intervention, though practical feasibility of this inclusion is a limitation.

The interviews aim to capture diverse perceptions of the intervention, utilising Normalisation Process Theory (NPT). This approach will facilitate mapping findings onto NPT's constructs: coherence (how the intervention is perceived and understood), cognitive participation (engagement and commitment of stakeholders), collective action (integration of the intervention into practice), and reflexive monitoring (ongoing assessment and adaptation of the intervention). Bracketing, reflexivity, and member checking will be integral to ensuring research trustworthiness and rigour.

Data will be analysed using NVivo software, employing an inductive approach without the constraint of existing theories, to allow for the natural emergence of findings. This analysis aims to identify critical elements of the intervention, explore implementation issues, and understand ethnicity and equity concerns. It will also focus on identifying perceived barriers or facilitators to implementation in usual practice. This inductive analysis, grounded in the data, will contribute valuable insights into the practicalities of the implementation process.

We propose to augment the qualitative analysis with the secondary quantitative analysis, detailed in the analysis section on page 19, to explore how content, compliance, and therapeutic alliance impact on the outcomes observed. A regression model will be conducted, with the primary outcome, number of offences in the previous 6-months, as dependent variable and adjusting for key covariates identified. This will allow for a quantification of what dimensions of the intervention are associated with outcomes and will enable an exploration of whether certain domains are more important than others and should be emphasised in the intervention delivery and, by extension, the training. Allied to this, we will assess the impact of staff turnover across the services, wellbeing of practitioners and the extent to which staff perceptions of working in a trauma informed manner, assessed using ARTIC 35, influences outcomes. In addition, the perception of therapeutic alliance will provide an insight into whether therapist communication style influences outcomes.

A secondary analysis, a Complier Average Causal Effects (CACE) model, will be conducted using an instrumental variable framework. CACE analysis allows us to avoid bias by weighting the ITT treatment effect by the dose of intervention or control treatment received, as a proportion of what was offered. This provides an unbiased estimate of the role of dosage in the outcomes observed. Compliance will address the extent to which those in the intervention group received the different elements of their allocated tier. By incorporating different quintile thresholds of dose, we can explore the nature of the relationship between compliance, dose, and outcomes observed.

In addition to this we would want to explore whether certain factors are associated with non-compliance to identify potential clusters of participants who do not comply. We will conduct a latent class analysis to identify clusters associated with non-compliance. This will enable an exploration of whether there are groups of participants who are harder to reach than others and by augmenting this quantitative approach with targeted qualitative interviews with young people and interventionists, enable the wider research group to explore what adaptations may be necessary to increase accessibility and compliance.

An aspect of our qualitative work with key stakeholders involves examining participants' positive and negative experiences of the allocation to different tiers of the intervention, exploring how these perspectives concur with those who conduct the trauma screening and allocate the participant to a tier, to explore at what points negative and positive experiences are at their greatest and what steps could be taken to ameliorate these experiences to improve the delivery and acceptability of the intervention. This information will be elicited as part of the semi-structured interviews.

The mechanism of change will be explored using a mediation model approach. Exploring factors that impact on the mechanism of change will be assessed using regression analysis to model the relationship between pre-randomisation factors and observed outcomes at 6 months. Interaction terms with allocation arm will be included in the analysis, and a significance level of 0.1 will be used to determine which factors are included in the regression model. Pre-randomisation factors include sex, age, ethnicity, IMD decile, number of adverse child experiences and family cohesion.

In addition to quantitatively understanding the mechanism of action, the qualitative analysis will provide an opportunity to explore the perceptions of the intervention from the point of view of a variety of stakeholders. The analysis will allow us to explore what elements of the interventions are useful and what elements are unnecessary, issues around how the interventions are planned and implemented and the perceived barriers or facilitators of implementation in usual practice.

Through a detailed exploration of the key dimensions, we plan on stating our logic model at the start of the project and revise this again at the end of the efficacy stage. The logic model will incorporate the qualitative research exploring stakeholder perceptions of acceptability and usefulness, hindrances and facilitators associated with the process and intervention but will also combine quantitative analysis exploring adherence, dosage, fidelity, and mediators associated with behaviour change. This mixed methods synthesis will enable us to understand what works, how it works, when it works and for whom it works and provide a detailed elaboration of the mechanisms and processes through which it works.

